August 16, 2022

Do Generic Volar Locking Plates Provide Similar Outcomes at a Reduced Cost?

Study Protocol and Statistical Analysis Plan

Study Narrative

1. Summary

Distal radius fractures are a common injury in the community. When treated with open reduction internal fixation (ORIF), the volar locking plate (VLP) is the most frequent implant used. Current literature has shown most orthopaedic surgeons are unfamiliar with construct costs. Many surgeons use implants the hospital provides and have no preference for one implant company's plate over another. Previous studies have demonstrated increased implant costs do not increase patient reported outcomes (PROs) in other injury patterns. Generic implants can potentially reduce total procedural costs and not negatively impact patient outcomes. With an increasing emphasis being placed on providing high-value care to patients, and rising healthcare costs, there is a need to pursue more economical means of treating distal radius fractures. Additionally, with the increasing volume of distal radius fractures with a growing elderly population, it is important to consider adoption of an already partially implemented process. Some surgeons today in our health system use the generic VLP, with little apparent differences in reoperation rates and complications. Validation of its safety and efficacy on a larger scale could support its adoption as a universal stand of practice, thus reducing cost to the patient and hospital.

2. Study aims:

- a. Primary:
 - i. To determine if there is any difference in 90-day reoperation rate between patients treated with a generic or conventional volar locking plate.
 - ii. To determine if there is any difference in 90-day readmission rate between patients treated with a generic or conventional volar locking plate.
 - iii. To determine if there is any difference in 90-day mortality rate between patients treated with a generic or conventional volar locking plate.

- b. Secondary:
 - i. To determine if generic implants have a lower cost than conventional implants.
 - ii. To determine any differences in estimated blood loss by implant type (generic vs. conventional).
 - iii. To determine tourniquet time by implant type (generic vs. conventional).

3. Background, Rationale, Significance

- a. Healthcare costs continue to rise in the United States, while Medicare reimbursement rates are declining (Haglin JOT 2021). With that, orthopaedic surgery is becoming a common target of cost containment strategies as musculoskeletal related procedures account for approximately one-quarter of surgical procedures performed in the United States (Seltzer JOT 2023). In addition, Medicare reimburses for roughly one-third of all orthopaedic procedures (Payne Am J Orthop 2015). One of the largest contributors to the overall cost of orthopaedic procedures is implant cost. On average implants attribute to 43-50% of procedure costs, and in some cases up to 87% of costs (Robinson JBJS 2012). Implant selection is also largely influenced by surgeons, although many are not aware of implant cost (Streit, Okike). With implants accounting for a large

proportion of overall cost, and being heavily determined by surgeons, implant-related cost reduction strategies such as using generic implants are critical to lowering costs in orthopaedic surgery.

Generic implant use has been shown to generate an average cost-savings of 49%, and in some cases up to 73% in orthopaedic trauma procedures (Kleinsmith COP 2024). Despite the reduction in cost related to generic implant use, it appears that there is still some concern among surgeons and patients over their quality and safety. One survey reported that 52% of the public see the value of generic implants, however only 26% would want them used in their surgery (Miner Ach Bone Surg 2022). Regarding surgeons, an OTA member survey found that many are aware of generic implants (73%), but only 26% use them in practice (Althausen 2016 JOT). Prior literature has compared generic cephalomedullary nails (CMNs) to brand name CMNs and found no difference in 6-month clinical and radiographic outcomes (Khoo JAAOS 2022, Kleinsmith 2024). Although this has been demonstrated in other injury patterns, there is a paucity of literature surrounding differences in cost and clinical outcomes associated with generic implant use in distal radius fracture (DRF) open reduction and internal fixation (ORIF).

DRFs are a prime target for generic implant implementation, due to the relatively high incidence of DRFs (634,000 annually) (Mauk Orthop Clin North America 2018), and the substantial amount spent by Medicare each year on DRF management (\$385-\$535 million) (Ray JBMR 1997, Burge JBMR 2007). The purpose of this study was to assess for differences in implant cost, surgical characteristics, and 90-day clinical outcomes between patients treated with generic volar locking plates (VLPs) and conventional VLPs in the setting of a DRF. We hypothesized that there would be no difference in surgical characteristics (e.g., tourniquet times) or clinical outcomes (e.g., reoperation), however there would be reduced cost in the generic VLP group.

4. Approach

a. Study design

- i. This will be a prospective randomized controlled trial within Healthpartners in the greater Minneapolis area in Minnesota, to compare primary outcomes of subjects between generic and conventional volar locking plates in distal radius fracture patients. Group selection will be randomized month to month with generic plates being used one month and conventional plates the next.

i. Inclusion

1. >18 years old
2. Isolated DRF
3. Medical need for surgical fixation with a volar locking plate

ii. Exclusion

1. No VLP used
2. Additional fixation used
3. Injury was non-isolated (polytrauma)
4. < 18 years old
5. Open fracture

- b. Data collection process
 - i. Identify patients within HealthPartners who meet inclusion criteria who are determined to need distal radius ORIF
 - 1. Patients meeting inclusion criteria will be identified by the included surgeons on the study
 - ii. Consent
 - 1. Written informed consent for surgery will be obtained by the attending surgeon, however no additional consent will be needed as this is an FDA approved device
 - iii. Data sources needed for this study
 - 1. Chart Review for patient age, gender, height and weight
 - 2. Chart review for mortality, reoperation, readmission
 - 3. Chart review for implants, tourniquet time, estimated blood loss
 - 4. Implants will be cross referenced with institutional charge master database to obtain cost.
 - iv. Process steps for data acquisition
 - 1. Data to be obtained by chart review after completion of the study.
- c. Intervention, treatments
 - i. Patients will be randomized by month with patients during one month receiving generic implants and the following month they receive conventional implants.
 - ii. All other standards of care remain equal between the groups.
- d. *Outcomes/endpoint and other variable definitions, and instruments used*
 - i. 90-day reoperation
 - ii. 90-day readmission
 - iii. 90-day mortality
 - iv. Implant cost
 - v. Estimated blood loss
 - vi. Tourniquet Time
- e. *Statistical analysis plan*
 - i. T-Tests and Chi-square of Demographic Data
 - ii. Chi-square of primary outcomes
 - 1. 90-day reoperation rate
 - 2. 90-day readmission rate
 - 3. 90-day mortality rate
 - iii. T-Test of Secondary Outcome Measures between subject groups
 - 1. Implant cost
 - 2. Tourniquet time
 - 3. Estimated blood loss
 - iv. Power analysis or statement of precision
An a priori power analysis was conducted to estimate the minimum sample size needed to adequately detect a difference in reoperation rates with a large effect size (Cohen's $d=0.8$). At a Type I error rate of 0.05, a power of 80%, and a 1:1

group allocation, the estimated sample size was 36 patients (18 generic VLPs vs. 18 conventional VLPs).

v. Strengths

1. Blinding of patients
2. Use of FDA approved devices
3. Randomizing of patients
4. Adequate qualified staff members to conduct the study
5. Surgeons will be adequately trained and reminded on the protocol and their specific research related duties.
6. High-volume surgeons who regularly treat distal radius fractures
7. Conservative effect size estimates

vi. Limitations

1. Surgeons are not blinded
2. Only early follow-up (90 days)
3. No patient reported outcomes included

5. Setting/Environment/Organizational feasibility

- a. This study will be conducted at Healthpartners within Minneapolis metropolitan area
- b. This HealthPartners setting has an appropriate patient population to carry out the proposed study.
- c. The orthopedic department leadership has been engaged in development and approval of this study

6. Risks and Benefits

- a. Potential risks
 - i. No different than associated risks of undergoing a standard DRF ORIF.
- b. Benefit to society
 - i. Being able to validate the use of cheaper implants to save cost for patients and healthcare systems.

7. Data Confidentiality and Privacy

- a. In order to secure patient confidentiality and data security, all data will be de-identified. All patients will be assigned a research identification number (not their MRN) that cannot be associated with their name, birthdate, or other identifying information.
- b. Patient information will only be accessed via secure servers for TRIA and on encrypted password-protected computers. If it is necessary to transmit patient data, it will be transmitted in the de-identified format, using only patient research identification numbers.
- c. At the end of the study, the electronic files will be permanently deleted and patient identifiers will be removed.

8. Timeline

- a. August 2022: IRB submission
- b. September 2022: IRB approval
- c. October 2022: Protocol implementation
- d. April 2023: Patient enrollment closes
- e. May 2023: Data analysis
- f. July 2023: Manuscript preparation

- g. July 2023: Manuscript submission
- 9. Dissemination/Sharing Results/Integration and Impact
 - a. We do plan on publishing to peer reviewed orthopedic journals such as;
 - i. The Journal of Bone and Joint Surgery
 - ii. Clinical Orthopedics and Related Research
 - iii. Journal of Orthopedic Trauma
 - b. We plan to disseminate the information on a local and regional level by presenting at;
 - i. University of Minnesota Grand Round
 - ii. Minnesota Orthopedic Society poster presentation
 - iii. Mid-America Orthopedic Society poster presentation
 - c. Results will be shared with HealthPartners

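### Plates are allocated by calendar month, but the aims compare patients by plate received and no rule says which arm an off-month patient belongs to

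*Combined protocol and SAP*

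**What the plan says.** All references are to the combined protocol and SAP.

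- **Allocation.** Section 4.a.i: "Group selection will be randomized month to month with generic plates being used one month and conventional plates the next". Section 4.c.i repeats it: "Patients will be randomized by month with patients during one month receiving generic implants and the following month they receive conventional implants". Assignment is therefore a property of the month.
- **Aims.** Section 2.a.i: "To determine if there is any difference in 90-day reoperation rate between patients treated with a generic or conventional volar locking plate". The readmission and mortality aims (2.a.ii–iii) are worded the same way. The blood-loss and tourniquet aims (2.b.ii–iii) compare by type of implant.
- **Analysis.** Section 4.e names t-tests and chi-square tests. For the secondary outcomes it refers only to groups of subjects. It contains no intention-to-treat, as-treated or per-protocol definition.
- **Data.** The only arm-related item in 4.b.iii is in the line "Chart review for implants, tourniquet time, estimated blood loss". Assigned plate, allocation month and surgery date are not listed. Section 4.b.iv adds: "Data to be obtained by chart review after completion of the study".
- **Blinding.** The limitations in 4.e.vi state: "Surgeons are not blinded".

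No section says whether off-month plates are expected, allowed or forbidden, or how such a patient is analysed.

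**The concern.** Suppose a patient has surgery in a generic month and the surgeon, who knows the plate, implants a conventional VLP. None of the exclusions in 4.a removes that patient on account of the switch: a VLP was used, and no additional fixation need be involved. The patient stays in the analysis, and the open question is on which side.

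An analyst working from the aims and the data list would most naturally use the implant found in the chart, which puts this patient in the conventional group. The choice of plate is the surgeon's and could plausibly follow fracture difficulty. The comparison would then depend partly on which patients were moved, and whatever protection the monthly allocation gives would be lost. The direction matters: moving difficult generic-month cases into the conventional group flatters the generic plate, and section 1 hopes to support its universal adoption.

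Leaving the rule unstated also allows the grouping to be chosen after the results are known.

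**Working it through.** The plan gives no figure for switching, so there is none to reproduce. The 18 per arm and d = 0.8 used below come from 4.e.iv; whether one follows from the other is a separate matter that does not affect this point.

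**1. Wording side by side**

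| Place | How groups are described |
|---|---|
| 4.a.i, 4.c.i | by month |
| 2.a.i–iii | by plate the patient was treated with |
| 2.b.ii–iii | by type of implant |
| 4.e | not specified |
| 4.b.iii | implant used is recorded; assigned plate and surgery date are not listed |

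**2. Selective switching, no true plate effect**

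Let q be the share of difficult fractures, s the share of difficult generic-month cases switched to conventional, and r_h and r_e the reoperation risks in difficult and other cases. By plate received:

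- generic = [q(1−s)r_h + (1−q)r_e] / (1 − qs)
- conventional = [q(1+s)r_h + (1−q)r_e] / (1 + qs)

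Assumed (not in the documents): q = 0.25 and switching one way only. Example with s = 0.4 (10% of generic-month patients), r_h = 8%, r_e = 1.333% (3% overall):

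- generic = (0.15×0.08 + 0.75×0.01333)/0.90 = 2.44%
- conventional = (0.35×0.08 + 0.75×0.01333)/1.10 = 3.45%
- difference = −1.0 point

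Generic minus conventional, by share of generic-month patients switched:

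| Assumption | 5% | 10% | 20% |
|---|---|---|---|
| Risks 8% / 1.3% (3% overall) | −0.5 | −1.0 | −2.1 points |
| Risks 12% / 2.7% (5% overall) | −0.7 | −1.4 | −2.9 points |
| Tourniquet time 20 min longer if difficult | −1.5 | −3.0 | −6.25 min |

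A smaller risk gap gives less: with 6% and 2%, the differences are −0.3, −0.6 and −1.25 points. If 10% or 20% are switched regardless of difficulty, the difference is 0. If difficult conventional-month cases were the ones switched, the sign would reverse.

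**3. A more extreme case at the planned size**

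Assumed: 18 per month-assigned arm, 3 difficult cases in each, all 3 generic-month difficult cases switched, risks 20% and 3%, tourniquet times 90 and 60 min.

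- Reoperation by plate received: generic 3.0%; conventional (15×0.03 + 6×0.20)/21 = 7.86%; difference −4.9 points (0.45 against 1.65 expected events).
- Reoperation by month: (15×0.03 + 3×0.20)/18 = 5.83% in both arms.
- Tourniquet by plate received: 60 against (15×60 + 6×90)/21 = 68.6 min. By month: (15×60 + 3×90)/18 = 65 min in both.
- With only one of the three switched: (15×0.03 + 2×0.20)/17 = 5.0% against (15×0.03 + 4×0.20)/19 = 6.6%, or −1.6 points.

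**4. Cost**

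Section 3.a cites an average saving of 49%, so set conventional = 100 and generic = 51. With 3 of 18 switched:

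- by plate received: saving 49%
- by month: (15×51 + 3×100)/18 = 59.2, saving 41%
- by month, if an opened generic set is also charged (assumed): (15×51 + 3×151)/18 = 67.7, saving 32%

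**5. Price of analysing by assigned month**

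One-way switching of a share w of generic-month patients multiplies a true effect by (1 − w). So d = 0.8 becomes 0.76, 0.72 and 0.64 at 5%, 10% and 20%, and 0.8×15/18 = 0.67 at 3 of 18.

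**The case against.** Much of the opposing case is fair.

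- **A reader might infer that the plan fixes as-treated arms.** It does not. Sections 4.a.i and 4.c.i describe month-based groups, 4.e is silent, and the wording of the aims is common in trials analysed either way. Grouping by plate received is the most natural reading of the aims and data list together, but it is not stated.
- **A reader might infer that assignment cannot be recovered.** The 90-day outcomes need a start date, presumably surgery, and the operative chart is reviewed anyway. Surgery date plus the month schedule would rebuild the assigned plate. That is itself an inference, since neither is listed; reasons for a switch could not be rebuilt this way, and 7.c has the electronic files deleted at the end of the study.
- **A reader might infer that every switch biases the results.** Only switching related to outcome risk biases the clinical comparisons. Section 1 says many surgeons take whichever implant is stocked and have no preferred maker, and that some in this system already use the generic plate. Against that, section 3.a says surgeons strongly influence implant choice and reports concern about generics. The rate and direction of switching are unknown.
- **The 3-of-18 scenario is severe.** It moves every difficult generic-month case and no others, with a nearly sevenfold risk gap. It also ignores difficult cases that might leave through the additional-fixation exclusion.
- **Aim 2.b.i can fairly be read as a device-price question.** A price comparison answers it. The cost of a generic-plate policy is a further question, not a correction.
- **Analysis by assigned month is not conservative here.** The hypothesis in section 3 is no clinical difference, and dilution moves results toward it. This stands, and it is why both analyses are needed.

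**Conclusion.** The point holds as an inconsistency between allocation and comparison, with no rule for off-month patients. It affects all three primary comparisons, blood loss and tourniquet time.

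Its size is conditional. With selective one-way switching of 5–20% of generic-month patients, a quarter of fractures difficult and overall reoperation of 3% or 5%, grouping by plate received creates a false difference of about 0.5 to 2.9 points in favour of generic. The harsher 3-of-18 scenario gives 4.9 points. With switching unrelated to risk, the clinical bias is zero. None of these rates is in the documents, so the figures show what could happen and do not predict it. Blood loss would be affected by the same mechanism; no figure was calculated for it.

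A reader might go further and conclude that the trial's results will be biased. The documents do not support that, because they neither fix the plate-received grouping nor say that switching will occur. Severity: should-fix.

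**What to change.** 1. **Groups.** In sections 2 and 4.e, define the groups for the three primary outcomes, blood loss and tourniquet time by the plate assigned to the month of surgery, whichever plate was implanted.
2. **Data.** Add surgery date, assigned plate for that month, plate implanted and reason for any switch to 4.b.iii.
3. **Reporting.** Give the number of off-month plates by assigned arm, with reasons. Report the plate-received analysis alongside the assigned-month analysis, because the hypothesis is no difference and the assigned-month analysis dilutes a true plate effect.
4. **Cost.** Keep the device-price comparison for aim 2.b.i. Add cost by assigned month, counting every implant charged, including any opened and discarded.

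The cost is a few sentences and a few fields, mostly from records already under review; the reason for a switch is best noted at the time of surgery. The statistical price is the dilution shown above, for example d from 0.8 to 0.72 at 10% switching. The change does not deal with the exclusions that depend on what was done at surgery, or with the predictability of monthly alternation; those are separate points.

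### Three 90-day outcomes are primary with no ranking or decision rule, though only reoperation was sized; mortality is the weakest, because 'no difference' on deaths at 18 per arm says almost nothing about the plate

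*Combined protocol and SAP*

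**What the plan says.** Section 2.a of the combined protocol and SAP sets out three primary aims in the same form of words:

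- "To determine if there is any difference in 90-day reoperation rate between patients treated with a generic or conventional volar locking plate"
- "To determine if there is any difference in 90-day readmission rate between patients treated with a generic or conventional volar locking plate"
- "To determine if there is any difference in 90-day mortality rate between patients treated with a generic or conventional volar locking plate"

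Section 4.e.ii ("Chi-square of primary outcomes") lists the same three rates, each to be tested. It gives no order of testing, composite, division of alpha or success rule, and no fallback for a table without events.

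Section 4.e.iv treats the three differently. Its sample size is meant to "adequately detect a difference in reoperation rates with a large effect size". It is set "At a Type I error rate of 0.05, a power of 80%, and a 1:1" allocation, giving 36 patients, 18 per arm. Readmission and mortality do not enter it.

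Section 4.a limits entry to isolated distal radius fractures and excludes polytrauma and open fractures. Section 3 hypothesises no difference in clinical outcomes, with reoperation as its example, and no margin is stated anywhere. Section 1 says that validating safety and efficacy could support universal adoption of the generic plate.

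**The concern.** With three unranked primary outcomes, the plan does not say what the trial's answer is if they point in different directions. The outcome it was sized for has no formal priority over the two it was not sized for.

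Mortality adds a second difficulty. The hypothesis is no difference and there is no margin, so a non-significant or empty mortality table could stand as one of three primary results in favour of similar outcomes. In this population, and with this number of patients, that result is close to guaranteed whether or not the plates differ. What is at stake is how much of the headline conclusion rests on a comparison that could hardly have come out otherwise.

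**Working it through.** **Inputs.** From the documents: 18 patients per arm, 36 in total, alpha 0.05 (Section 4.e.iv); a chi-square test for each primary outcome (4.e.ii); the aims ask about any difference, so two-sided (2.a). Assumed: 90-day mortality of 0.5%, 1% and 2%, because the documents give no event rate for any of the three outcomes.

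**The plan's own figure.** A two-sided t-test with d = 0.8, alpha 0.05 and 80% power needs 26 per arm (52 in total), not 18; at 18 per arm its power is 64.5%. The stated 36 is therefore not reproduced on that basis. That is a separate matter; 18 per arm is taken as given below.

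**1. Chance of no deaths in either arm.** With the same rate p in both arms, P(no deaths) = (1 − p)^36.

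| Assumed mortality | P(no deaths in 36) |
|---|---|
| 0.5% | 0.995^36 = 0.835 |
| 1% | 0.99^36 = 0.696 |
| 2% | 0.98^36 = 0.483 |

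With no deaths, the expected counts in the death column are zero and the planned chi-square cannot be computed.

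**2. What an empty arm excludes.** The exact two-sided 95% upper limit for 0 of 18 is 1 − 0.025^(1/18) = 1 − 0.815 = 0.185. A true mortality of up to 18.5% in that arm remains compatible with the data.

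**3. What it takes to reach significance.** With no deaths in one arm, the uncorrected chi-square p-value is 0.070 for 3 of 18 deaths in the other and 0.034 for 4 of 18. At least 4 of 18 (22%) is needed.

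**4. Chance of a significant result.** This sums the binomial probabilities of every 18 v 18 table with uncorrected p < 0.05.

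| True mortality | P(p < 0.05) |
|---|---|
| 1% v 1% | under 0.0001 |
| 2% v 2% | 0.0005 |
| 1% v 3% | 0.0015 |
| 2% v 6% | 0.014 |

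Even if mortality were tripled in one arm from 2%, the test would fail to reach significance 98.6% of the time.

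**5. The same check on reoperation.** At assumed true rates of 5% v 10%, P(p < 0.05) = 0.043. With a reoperation rate of 2% or 3% in both arms, the chance of no events in 36 is 0.98^36 = 48% or 0.97^36 = 33%. Reoperation also says little at this size.

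**6. Multiplicity at realistic rates.** The same enumeration under equal rates gives a rejection probability of 0.0005 at 2%, 0.009 at 5% and 0.033 at 10%. If the three outcomes are independent:

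- Rates of 5%, 10% and 2% for reoperation, readmission and mortality: 1 − 0.991 × 0.967 × 0.9995 = about 4%.
- Rates of 10%, 10% and 5%: 1 − 0.967 × 0.967 × 0.991 = about 7%.

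**The case against.** **The change does not cure the harm.** Step 5 shows that reoperation shares the weakness, so moving mortality out of the primary set leaves a primary outcome that is itself nearly uninformative. This stands. The root problem is the sample size and the missing margin. It limits what the fix achieves, but it is no reason to keep a further, weaker null among the primary results.

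**The ranking is already discernible, and safety belongs in the headline.** Reoperation is the example in the hypothesis and the only outcome in the power statement, and the stated purpose includes safety. Part of this stands: deaths should be collected and reported prominently. But a lead outcome that has to be inferred is not a decision rule, and safety reporting does not require primary status.

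**The misuse is a forecast.** The plan does not say that an empty mortality table will be claimed as similarity. That is correct. The risk is inferred from the title, the no-difference hypothesis and the absence of a margin.

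Two stronger readings are tempting and are not supported:

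- A reader might infer that three tests at 0.05 inflate the family error to 1 − 0.95³ = 14%. That assumes each test attains its nominal 5%. With rare events and 18 per arm it does not, and step 6 puts the error at about 4% to 7%. The problem is an uninformative null, not false positives.
- A reader might infer that readmission is as remote from the plate as death. The documents define neither readmission nor its causes, and it can include plate-related complications. The case for moving it rests on its being unsized and unranked, not on irrelevance.

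**Conclusion.** The point holds. Three primary outcomes without ranking or decision rule follow directly from Sections 2.a and 4.e.ii, and sizing for reoperation alone follows from 4.e.iv; none of this depends on an assumption.

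That mortality is the weakest of the three rests on two further elements. One is an assumed 90-day mortality of 0.5% to 2%, which gives an 83% to 48% chance of no deaths at all; the upper limit of 18.5% for 0 of 18 needs no assumed rate. The other is the clinical inference that deaths after a closed, isolated wrist fracture mostly reflect age and other illness; the documents neither state nor contradict it, and the arithmetic does not need it.

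This is an inexpensive improvement to what the trial may claim. A reader might infer that, once it is made, a null result on reoperation would show the plates to be similar. It would not: at 5% v 10% the test is significant only about 4% of the time.

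**What to change.** 1. In Sections 2.a and 4.e.ii, name 90-day reoperation as the single primary outcome, in line with the power statement in 4.e.iv.
2. Reclassify 90-day mortality and readmission as safety outcomes, reported as counts by arm with exact confidence intervals. Give the reasons for each readmission, so that plate-related complications can be seen.
3. State in the SAP that a null or empty mortality comparison is not evidence of similarity.
4. Acknowledge that these changes do not make a null result on reoperation informative at 18 per arm. Sample size and a margin have to be dealt with separately.

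**Cost.** Rewording of two sections, with no extra patients or visits; recording reasons for readmission may need one more chart-review field. The sponsor gives up two primary claims. Section 8 schedules analysis for May 2023, so if outcome data have already been examined, the re-ranking should be dated and disclosed as made after that.

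### The trial is called randomised and lists randomisation of patients as a strength, but its only allocation rule is alternation of plate type by calendar month

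*Combined protocol and SAP*

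**What the plan says.** Section 4.a gives the design label: "This will be a prospective randomized controlled trial within Healthpartners". The allocation rule appears in two places and nowhere else:

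- Section 4.a: "Group selection will be randomized month to month with generic plates being used one month and conventional plates the next".
- Section 4.c.i: "Patients will be randomized by month with patients during one month receiving generic implants and the following month they receive conventional implants".

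The strengths in section 4.e.v include "Randomizing of patients". The limitations in section 4.e.vi include "Surgeons are not blinded", but not the alternating or predictable allocation.

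On recruitment, section 4.b.i says: "Patients meeting inclusion criteria will be identified by the included surgeons on the study". The exclusions in section 4.a include cases in which no volar locking plate is used, and "Additional fixation used". The patient characteristics to be collected (section 4.b.iii) are limited to one item: "Chart Review for patient age, gender, height and weight". Section 4.e plans t-tests and chi-square tests of demographics, chi-square tests of the three primary outcomes, and t-tests of implant cost, tourniquet time and blood loss. Section 8 puts implementation in October 2022 and close of enrolment in April 2023.

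**The concern.** Randomisation protects a comparison in two ways: nobody can foresee the next assignment, and chance alone links the assignment to patient characteristics. Month-by-month alternation gives neither. The surgeon who judges eligibility knows this month's plate and next month's. Whether a volar plate is used, and whether extra fixation is added, is settled at surgery with the arm known. If either decision differed by plate type, the analysed groups would differ in case mix, and the plan does not provide for reporting exclusions by arm.

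A second, weaker point concerns the analysis. The t-tests treat patients as independently allocated, while only 6 or 7 months are allocated. Anything that makes patients in the same month alike, such as staffing or case mix, could then be read as a plate effect on tourniquet time or blood loss.

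The stake is what the trial can claim. Section 1 hopes the results will support wide adoption of generic plates and section 9 plans publication, so readers would rely on the randomised label.

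**Working it through.** **1. Is any random element described?** Sections 4.a and 4.c.i both use the word randomised, and both then define the scheme as one plate type in one month and the other in the next. No section mentions a sequence generator, a random order of months, a random starting plate, blocks or concealment. Everyone treated in a given month is due the same plate type, so no individual patient is randomised.

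**2. How predictable is it?** October 2022 to April 2023 gives 6 or 7 monthly blocks, depending on whether April counts. Alternation allows at most 2 sequences, and the first month identifies which one. A random balanced order of 6 months would have 6!/(3! × 3!) = 20.

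**3. Scale of month effects (illustration only).** The documents give no intra-month correlation (ICC), so 0.02, 0.05 and 0.10 are assumed. N = 36 comes from section 4.e.iv, where it is a minimum.

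Hand check with k equal, independent months: design effect = 1 + (N/k − 1) × ICC. For N = 36, k = 6, ICC = 0.05 this is 1 + 5 × 0.05 = 1.25. The two-sided 5% critical value on 34 df is 2.032, and 2.032/√1.25 = 1.818, giving a true rejection rate of about 7.8%.

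Simulation (36 patients spread at random over alternating months, normal outcome, no plate effect, pooled t-test, 60,000 runs) gives these Type I error rates:

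| Month effects | Months | ICC 0.02 | ICC 0.05 | ICC 0.10 |
|---|---|---|---|---|
| Independent | 6 | 6.3% | 8.4% | 11.7% |
| Independent | 7 | 6.2% | 7.9% | 10.9% |
| AR(1), 0.5 | 6 | 5.6% | 6.2% | 7.6% |
| AR(1), 0.5 | 7 | 5.5% | 6.0% | 7.3% |
| AR(1), 0.8 | 6 | 5.4% | 5.6% | 6.2% |
| AR(1), 0.8 | 7 | 5.0% | 5.5% | 5.8% |

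**4. Smooth drift.** With 7 months, one arm has months 1, 3, 5, 7 (mean 4) and the other 2, 4, 6 (mean 4), so a linear trend cancels. Simulated size is 5.0% and 4.8% at trend variance shares of 0.05 and 0.10. With 6 months the means are 3 and 4, so one month of trend remains: 6.5% and 8.2%.

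**5. Larger enrolment.** Section 8 closes enrolment by date and no cap is stated. At an assumed N = 120, ICC 0.05 and independent months, the design effect is 1 + 19 × 0.05 = 1.95 for 6 months, and 1.980/√1.95 = 1.418 gives about 15.9%. Simulation over 6 or 7 months gives about 15-17%.

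**6. Scale of selection (illustration only).** Remove 1, 2 or 3 of 18 patients from one arm only, using a score with an assumed correlation with tourniquet time. Type I error is 5.3%, 5.3% and 5.8% at correlation 0.3, and 5.3%, 6.2% and 7.3% at correlation 0.5.

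**7. Can the demographic comparison stand in for randomisation?** A two-sided 5% t-test at 18 versus 18 has power 9.0%, 30.8% and 64.5% for true imbalances of 0.2, 0.5 and 0.8 SD. It is a partial check on a short list of characteristics.

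**The case against.** The strongest defence of the label is that randomising month to month might mean a random order of months, or a random starting plate. The rest of each sentence rules out a random order. An undocumented random start would still leave two possible sequences, each fully known after month one, and patients would still not be randomised.

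The better objection concerns harm. Section 4.b.ii requires no separate study consent, so there is no consent step at which patients could be steered or could refuse by arm. Section 4.e.v lists surgeon training and patient blinding, and section 4.c.ii holds other care equal. Section 1 says many surgeons have no plate preference, although section 3 reports some concern about generics. The two exclusions settled at surgery apply to both arms and bias the comparison only if used differently. All of this stands. It narrows the routes to bias, but it creates no randomisation and does not stop an operation being timed.

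Three stronger readings are tempting and not supported:

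- A reader might infer that the comparison is biased. The documents show opportunity, not differential selection, and every error rate above rests on assumed inputs.
- A reader might measure the problem by the share of patients treated in months whose arm was foreseeable: with even accrual, 36 × 5/6 = 30 or 36 × 6/7 ≈ 31 of 36. That is only months minus one over months. It does not measure bias, and the documents do not say how far surgery can be deferred.
- A reader might carry the inflated t-test error over to the primary outcomes or to cost. The calculations concern a continuous outcome such as tourniquet time or blood loss, and do not support that step.

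**Conclusion.** The concern holds as a statement about the design. The plan claims randomisation of patients and describes alternation of months. This follows from the text alone, needs no assumption, and can be held with high confidence. It should be fixed because it determines what kind of evidence the trial can claim to provide.

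The effect on results is plausible but unproven, and is confined here to two secondary outcomes. With 36 patients, the t-test's Type I error ranges from essentially nominal (serially correlated months at ICC 0.02, or a linear trend over 7 months) to 11.7% (6 independent months, ICC 0.10). It rises further if enrolment exceeds the stated minimum. These figures depend on the assumed ICC, serial correlation, number of months and N. They indicate scale and do not establish bias.

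**What to change.** 1. **Wording.** Describe the design as quasi-randomised (alternating calendar months) in sections 4.a and 4.c, and delete randomisation of patients from the strengths. Add predictable allocation and the small number of allocated months (6 or 7) to the limitations. Conclusions should not be presented as those of a patient-randomised trial. This costs nothing beyond the edit.
2. **Reporting.** From charts or theatre records, list all distal radius ORIF patients in each study month. Report eligibility and exclusions, including no volar plate and additional fixation, by scheduled arm. Keep the month of surgery in the analysis file. The operation date is already needed for 90-day outcomes, but month is not among the data items in section 4.b.iii. This must be done before the de-identification in section 7.a and the file deletion in section 7.c. The cost is some extra chart review of excluded cases.
3. **Optional analysis.** Keep the planned t-tests and add a month-level sensitivity analysis of tourniquet time and blood loss, using month means or a mixed model with a month random effect and small-sample degrees of freedom. Report estimates with confidence intervals and make no conclusion depend on it. Its precision is low: with 36 patients and d = 0.8, the month-means test has power of about 30-43%, against about 61-65% for the patient-level t-test in the same simulations. The plan should say so.
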